9.1 Hypotheses

Null Hypothesis: No difference in shoulder ROM or pain levels between the three groups.

Alternative Hypothesis: VR-assisted rehabilitation leads to superior improvements in ROM and pain reduction compared to traditional rehabilitation and control.

9.2 Sample Size

A total of 45 participants (15 per group) will be recruited to ensure adequate statistical power (80%) to detect significant differences.

9.3 Statistical Analyses

Primary Analysis: Repeated-measures ANOVA to compare pre- and post-intervention ROM across the three groups.

Secondary Analysis: Post hoc Tukey HSD comparisons to assess pairwise differences between groups.

10. Ethical Considerations

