2.1 Study Rationale

Shoulder injuries are common in sports, particularly in basketball, and can significantly impact athletic performance and recovery. Traditional rehabilitation methods often lack engagement and personalized feedback, potentially hindering recovery. Virtual Reality (VR) offers a unique, immersive environment for rehabilitation, potentially improving adherence, engagement, and outcomes. This study aims to assess whether VR-assisted rehabilitation can offer superior results in improving shoulder ROM and reducing pain compared to traditional methods.

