4.1 Overall Design

This study will be a randomized controlled trial (RCT) with three groups: VR-assisted rehabilitation, traditional rehabilitation, and a control group. Participants will be randomly assigned to one of the three groups. Pre- and post-intervention measurements of shoulder ROM and pain levels will be collected.

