4.2 Scientific Rationale for Study Design

The randomized controlled design minimizes bias and allows for clear comparisons between the groups. By using a control group, we can assess whether the VR intervention leads to improvements beyond the natural progression of rehabilitation or training.

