4.3 Justification for Intervention

Given the potential of VR to engage participants and provide interactive, task-specific rehabilitation, it is hypothesized that VR-assisted rehabilitation will lead to greater improvements in shoulder ROM and pain reduction compared to traditional methods.

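### Section 9.3 makes a three-group pre/post ANOVA primary and the two VR contrasts that carry the hypothesis secondary; ANCOVA on the baseline ROM already collected would usually be more precise.

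*Protocol*

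**What the plan says.** Protocol section 9.3 has two lines. The first is "Primary Analysis: Repeated-measures ANOVA to compare pre- and post-intervention ROM across the three groups". The second, labelled secondary, is "Post hoc Tukey HSD comparisons to assess pairwise differences between groups". No baseline covariate is named.

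The question put elsewhere is about specific pairs:

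- Section 9.1, alternative hypothesis: "VR-assisted rehabilitation leads to superior improvements in ROM and pain reduction compared to traditional rehabilitation and control".
- Section 4.3, VR against traditional: "it is hypothesized that VR-assisted rehabilitation will lead to greater improvements in shoulder ROM and pain reduction compared to traditional methods".
- Section 2.1, the same comparison: "VR-assisted rehabilitation can offer superior results in improving shoulder ROM and reducing pain compared to traditional methods".
- Section 4.2, on the purpose of the control arm: "we can assess whether the VR intervention leads to improvements beyond the natural progression of rehabilitation or training".

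The primary objective in section 3.1 names no comparator, and the null in section 9.1 is a three-group null. On data, section 4.1 says "Pre- and post-intervention measurements of shoulder ROM and pain levels will be collected", and the timeline in section 11 places baseline ROM before the intervention. On size, section 9.2 says "A total of 45 participants (15 per group) will be recruited to ensure adequate statistical power (80%) to detect significant differences" without naming the test or contrast to which the power belongs.

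**The concern.** There are two linked problems.

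First, the test that ranks as primary is not the test that answers the question. A three-group test can reject for any pattern among the arms, including one in which VR is no better than traditional rehabilitation or does nothing. A positive primary result could then be reported beside a VR claim that rests only on secondary comparisons, or on none.

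Second, the planned model uses the baseline only by subtraction. When the regression slope of post on pre ROM is away from 1, subtraction adds noise that adjustment would remove. With 15 per arm there is little precision to spare.

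**Working it through.** **Inputs.** From the protocol: 15 per arm, 45 in total (9.2); pre and post ROM (4.1); three-group repeated-measures ANOVA, then Tukey over all pairs (9.3). Not given, so assumed: two-sided alpha 0.05; pre-post correlation r; post/pre SD ratio k.

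**1. The plan's own figure.** The 80% in 9.2 cannot be reproduced, because no alpha, effect size or SD is stated. Solved backwards, 45 participants give 80% power for f = 0.48 in the three-group test on change, or for a difference of 1.20 change-score SDs in one Tukey contrast. These are different targets, and 9.2 does not say which is meant.

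**2. Does the three-group test answer the VR question?** Simulation, 20,000 trials per row, true mean changes in change-score SDs:

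| VR / traditional / control | Three-group test rejects | Tukey: VR > traditional | Tukey: VR > control | Both |
|---|---|---|---|---|
| 1.2 / 1.2 / 0 | 91.8% | 1.0% | 80.2% | 1.0% |
| 0 / 1.2 / 0 | 91.5% | 0.0% | 1.1% | 0.0% |
| 1.2 / 0.6 / 0 | 82.1% | 22.6% | 80.3% | 21.8% |
| 1.2 / 0 / 0 | 91.7% | 80.2% | 80.2% | 69.2% |

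The primary test rejects about equally often whether VR beats both arms, matches traditional, or has no effect. This result needs no assumption about r or k.

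**3. Precision.** With two time points the group-by-time F is a one-way ANOVA on change. In units of the post SD squared:

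- Change scores, 42 df: 1 + 1/k² − 2r/k = (1 − r²) + (r − 1/k)².
- ANCOVA, 41 df: (1 − r²)(1 + 1/40), where 1/40 = 1/(45 − 3 − 2) is the expected cost of chance baseline imbalance.

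The extra term (r − 1/k)² is zero only when the slope rk equals 1, so the variance ratio cannot exceed 1.025. Example, k = 1, r = 0.5: 0.75 × 1.025 = 0.769 against 2 − 1 = 1.00, a ratio of 0.77.

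| ANCOVA/change variance ratio | r = 0.3 | 0.5 | 0.7 | 0.9 |
|---|---|---|---|---|
| k = 1 | 0.67 | 0.77 | 0.87 | 0.97 |
| k = 0.8 | 0.51 | 0.59 | 0.64 | 0.62 |
| k = 1.25 | 0.80 | 0.92 | 1.005 | 0.97 |

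At k = 1.25 and r = 0.8 the slope is exactly 1 and the ratio is 1.025.

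Break-even solves (r − 1/k)² = 0.025(1 − r²). ANCOVA is no better for r above 0.951 (k = 1), 0.818 to 0.956 (k = 1.1), 0.685 to 0.876 (k = 1.25) and 0.533 to 0.768 (k = 1.5).

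**4. Power for one VR contrast.** Tukey critical t for three groups is 2.432 (41 df) or 2.429 (42 df). ANCOVA reaches 80% at noncentrality 3.288, that is, a difference of 3.288 × √[(1 − r²) × 1.025 × 2/15] = 1.16 / 1.05 / 0.87 / 0.53 post SDs at r = 0.3 / 0.5 / 0.7 / 0.9. Tukey on change scores at the same differences has:

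| Power on change scores | r = 0.3 | 0.5 | 0.7 | 0.9 |
|---|---|---|---|---|
| k = 1 | 60.3% | 67.5% | 73.6% | 78.9% |
| k = 0.8 | 47.8% | 53.9% | 58.5% | 56.9% |
| k = 1.25 | 69.7% | 76.0% | 80.3% | 78.9% |

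Anchored the other way (k = 1, planned change-score contrast at 80%), ANCOVA at the same 45 participants gives 94 / 90 / 86 / 81%, falling to 79% at r = 0.99.

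**5. Power for both VR contrasts.** With VR better than both arms by the step 4 difference and k = 1 (40,000 simulated trials per cell), Tukey-adjusted ANCOVA shows both in about 69%. Change scores show both in 45.0 / 53.0 / 60.7 / 67.2%.

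**The case against.** The strongest reply has four parts.

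- *The model is not wrong, and it matches the null.* Read as group-by-time, the ANOVA is valid and unbiased in a randomised trial, and the null in 9.1 is a three-group null. Both statements are true. But rejecting that null does not support the directional alternative stated beside it.
- *The contrasts are already planned with error control, and an SAP could add a covariate.* The first part is true, so for the contrasts the change is one of rank, intervals and a decision rule. The SAP argument is weaker: 9.3 itself fixes the primary model and the order of the tests, and an SAP that reversed them would contradict the protocol.
- *The gain is unknown.* This stands. The protocol gives neither r nor SDs, and the range shown runs from a 49% variance reduction to a 2.5% loss; at r = 0.9 with equal SDs the gain is about 3% in variance and one point of power. What can be said is that the loss is capped and the gain is not small over most of the range.
- *Tukey is stricter than the joint claim needs.* Also true: if both contrasts must succeed, each can be tested at the unadjusted level. Unadjusted change scores then show both in 62 / 70 / 76 / 81% of trials, against 69% for Tukey-adjusted ANCOVA. That compares two different critical rules. Under the same unadjusted rule ANCOVA reaches 83%. The adjustment is still needed for a claim against a single comparator.

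Two side matters leave the point intact: section 11 lists both an initial and a final baseline evaluation, and section 14 gives n = 40.

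**Conclusion.** The concern holds and should be fixed, though it is not a matter of bias. The ranking problem is read directly from 9.3 against 9.1 and is the firmer half: the primary test can succeed in over 90% of trials when VR is no better than traditional rehabilitation. The precision problem is real but of uncertain size. ANCOVA is usually more precise, by a third in variance at r = 0.3 and 3% at r = 0.9 with equal SDs, and by more if ROM is less variable after treatment. It brings nothing where the pre-post slope is near 1. These figures rest on two-sided alpha 0.05, 15 per arm with complete data, a common linear pre-post slope, and assumed r and SD ratios.

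**What to change.** Rewrite 9.3 as follows.

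- For each ROM movement analysed as primary (section 8.1 lists five), fit an ANCOVA of post-intervention ROM on group and the baseline value of the same movement. State which of the baseline readings in section 11 is used.
- Make VR minus traditional and VR minus control the primary contrasts, each with a 95% confidence interval and the Tukey adjustment over three pairs that 9.3 already plans.
- Let a claim of superiority over one comparator rest on its own contrast, and require both contrasts for the full alternative in 9.1.
- Keep the repeated-measures ANOVA as a supportive analysis.

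Section 9.2 should then say which contrast its 80% refers to.

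The cost is wording, one degree of freedom, and at most about 2.5% in variance if the slope turns out near 1. No new data are needed. The error rate per movement stays at 5%, as with one three-group test per movement; how the five movements share it is a separate question that this change does not settle.

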3.2 Secondary Objectives

To compare the impact of VR rehabilitation and traditional rehabilitation on pain levels (measured using the Visual Analog Scale (VAS)).

To evaluate participant engagement and adherence to rehabilitation protocols in both VR and traditional rehabilitation groups.

4. Study Design

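### Section 9.1 claims VR is superior to both comparators, but the primary test in 9.3 is a three-group omnibus ANOVA that does not test that claim; the two VR comparisons that do are ranked secondary

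*Protocol*

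**What the plan says.** Protocol 9.1 sets the null "No difference in shoulder ROM or pain levels between the three groups" against the alternative "VR-assisted rehabilitation leads to superior improvements in ROM and pain reduction compared to traditional rehabilitation and control". Section 9.3 then gives the primary analysis as "Repeated-measures ANOVA to compare pre- and post-intervention ROM across the three groups" and the secondary analysis as "Post hoc Tukey HSD comparisons to assess pairwise differences between groups". No contrast is named as primary.

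Each comparator has a purpose of its own. Section 2.1 sets VR against traditional care: "This study aims to assess whether VR-assisted rehabilitation can offer superior results in improving shoulder ROM and reducing pain compared to traditional methods". Section 4.3 repeats this as the hypothesis. Section 4.2 justifies the control arm: with it, "we can assess whether the VR intervention leads to improvements beyond the natural progression of rehabilitation or training". Section 3.1, the primary objective, names ROM but no comparator. Section 3.2 covers pain between two arms only: "To compare the impact of VR rehabilitation and traditional rehabilitation on pain levels".

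Section 9.2 gives 45 participants, 15 per group, and 80% power, without saying for which test or effect. Section 8.1 defines the primary outcome as ROM in five directions.

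**The concern.** The null and the alternative in 9.1 are not complements. Many states of nature make both false: VR equal to traditional with both better than control, or traditional better than the other two arms. In each of these the omnibus null is rightly rejected, and the rejection says nothing in favour of VR. The result declared primary therefore does not answer the question that 9.1, 2.1 and 4.3 put, and the comparisons that do answer it rank below it. A trial could report a positive primary analysis while its central claim is unsupported or contradicted. The 80% power in 9.2, if it refers to the omnibus test, would also overstate the chance of establishing that claim.

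**Working it through.** **Inputs from the protocol.** Three groups, 15 per group (9.2); two measurement times, before and after (4.1, 9.3).

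**Assumptions, because the protocol gives no value.** Alpha 0.05, two-sided pairwise tests, no dropout, one ROM measure, SD of the change score = 1, and the group-by-time term as the ANOVA test of interest. With two time points that term equals a one-way ANOVA on change scores with 2 and 42 df.

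**The plan's own figure.** The 45 cannot be reproduced, since alpha, effect, SD and pre-post correlation are not stated. One set of assumptions comes close: a group-by-time test with f = 0.25 and correlation 0.5 needs N = 42 and has 83% power at 45. Other correlations move the answer widely (N = 81 at 0, N = 27 at 0.7), so this shows neither that 45 is right nor that it is wrong.

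**Omnibus power.** Noncentrality = n × Σ(μᵢ − μ̄)². Patterns are (VR, traditional, control) in SD units.
- One arm differing from two equal arms by d: Σ = (2/3)d². With d = 1.018, 15 × (2/3) × 1.036 = 10.36, which gives 80% power. This holds whichever arm differs, and in either direction.
- Equally spaced arms (d, d/2, 0): Σ = d²/2. With d = 1.175, 15 × 0.690 = 10.35, again 80%.
- (0.5, 1, 0): 15 × 0.5 = 7.5, which gives 65%.

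The value 1.02 was chosen to give 80%; it is not a protocol figure.

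**Decision rules compared.** Simulated trials with pooled variance on 42 df; critical t is 2.02 unadjusted and 2.43 for Tukey. The last two columns require VR to be better than both comparators.

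| Pattern | 9.1 alternative true? | Omnibus significant | Both contrasts at 0.05 | Both Tukey |
|---|---|---|---|---|
| (1.02, 1.02, 0) | no | 80% | 2.5% | 1% |
| (0, 1.02, 0) | no | 80% | 0% | 0% |
| (0.5, 1, 0) | no | 65% | under 0.1% | under 0.1% |
| (1.02, 0, 0) | yes | 80% | 66% | 49% |
| (1.18, 0.59, 0) | yes | 80% | 34% | 21% |

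At (1.02, 1.02, 0) the omnibus is significant without a Tukey result for VR over traditional in 79% of trials (80% less 1%). In 63% Tukey shows VR above control but not above traditional.

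**Five directions.** Requiring both contrasts needs no alpha split for a single measure: the false-claim rate stays at about 2.5% even at (5, 5, 0). If any one of the five directions in 8.1 may carry the claim, the rate at (1.02, 1.02, 0) is about 12%, 9% and 8% for inter-direction correlations of 0, 0.5 and 0.7.

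**The case against.** An omnibus ANOVA followed by Tukey HSD is a conventional sequence. It includes both VR comparisons and controls the error rate over all three pairs of one outcome. Section 9.1, read plainly, joins the two comparators with an *and*, so a split Tukey result does not meet it. Contrast definitions and rules for combining results may also sit in the statistical plan, which is not at hand. All of this stands, and it rules out two stronger readings. A reader might infer that the trial's conclusion is undefined; the wording of 9.1 shows that it is not. A reader might also take the 79% as a false-positive rate; it is not, because Tukey wrongly favours VR over traditional in only about 1% of those trials.

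What the objection does not remove is the ranking. The hypotheses and the primary and secondary labels are protocol text, and a statistical plan could cure the mismatch only by overriding them.

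It can further be said that requiring both contrasts is one choice among several. Section 3.1 names no comparator, 2.1 and 4.3 name only traditional methods, and under a joint rule the control question in 4.2 gets no separate primary answer. That is fair. The joint rule is preferred because it is what 9.1 says; a single VR-versus-traditional primary contrast would require 9.1 to be reworded.

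**Conclusion.** The point holds as a mismatch between the stated alternative and the test declared primary. The logical gap does not depend on any assumed number. Its illustrated size (omnibus significant in 80% of trials at (1.02, 1.02, 0) and at (0, 1.02, 0), where the 9.1 alternative is false) rests on the assumed alpha, SD, effects and single ROM measure.

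Three inferences go further than the document allows. No inflated error rate is shown under the current plan. The sample size of 45 is not shown to be wrong, because its inputs are not given. And although 9.1 mentions pain, it does not follow that pain needs the same two-comparator rule: 3.2 compares pain only between VR and traditional rehabilitation.

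**What to change.** In 9.3, name VR minus traditional and VR minus control in ROM change, from the same ANOVA model, as the primary contrasts. State that VR superiority in ROM is claimed only if both favour VR at two-sided 0.05. Keep the omnibus test and the three-way Tukey comparisons as secondary. Apply the rule to one named ROM measure, or adjust for multiplicity across the five directions in 8.1; without one of these, the rule would raise the false-claim rate. Leave pain as the secondary comparison in 3.2. In 9.2, say what the 80% refers to and restate it for this rule with its assumed effect, without enlarging the trial.

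The text change is a few sentences; the cost lies in the power statement. The rule has less power than the omnibus test, though more than requiring both Tukey comparisons. At 15 per arm it reaches 80% only if VR exceeds both arms by about 1.17 SD or, with traditional midway, exceeds control by about 2.10 SD and traditional by 1.05 SD. For one measure, its false-superiority rate when VR equals traditional is about 2.5%, against about 1% with Tukey.

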10.1 Ethical Approval

This study has been reviewed and approved by the Ethics Review Committee of Sanming Medical and Polytechnic Vocational College. The ethical approval process follows the guidelines set forth by the Institutional Review Board (IRB) to ensure the protection of participant rights and welfare throughout the research process.

10.2 Informed Consent

Participants will receive a comprehensive Informed Consent Form in Chinese and English, detailing the study's purpose, procedures, potential risks, and benefits. The form will also ensure participants are aware of their rights, including the right to withdraw at any time without penalty. A signed informed consent form will be obtained from all participants.

10.3 Participant Protection

The study ensures participant protection through:

Minimizing Risk: Interventions are non-invasive, with regular monitoring for any adverse effects.

Confidentiality: All data will be anonymized and securely stored.

Ethical Oversight: The study adheres to the Declaration of Helsinki and national ethical guidelines.

11. Participant Timeline

Stage	Timeline	Description
Recruitment	July 15 • July 18, 2024	Participants are recruited, screened, and provided with the informed consent form.
Screening and Baseline Assessment	July 19 • July 21, 2024	Initial assessments of shoulder ROM and pain levels (VAS), confirmation of eligibility.
Pre-Intervention Evaluation	July 22, 2024	Final baseline evaluation and randomization of participants into intervention groups.
Intervention Period	July 22 • September 9, 2024	Participants undergo 9 weeks of VR-assisted or traditional rehabilitation, or no intervention (control group).
Mid-Point Evaluation	August 15, 2024	Mid-intervention check-in to assess progress, adherence, and potential adjustments.
Post-Intervention Evaluation	September 10 • September 13, 2024	Final assessments of shoulder ROM and pain levels, along with participant feedback on engagement.
Follow-Up	September 13, 2024	Final data collection and study conclusion.

12. Data Management Plan

All participant data, including demographic information, assessment results (range of motion and pain scores), and session attendance, will be collected and recorded on standardized data collection forms. Each participant will be assigned a unique study ID number to ensure confidentiality.

Data Handling Procedures:

- Paper-based data will be digitized and stored in a password-protected, encrypted database on a secure personal computer accessible only to the research team.
- Electronic data will be backed up weekly on an encrypted external hard drive.
- All personal identifiers will be removed from the dataset before analysis.
- Only de-identified data will be shared in publications or public databases.

Data Integrity and Quality Control:

- Double data entry will be employed to reduce transcription errors.
- Data will be periodically reviewed for completeness and consistency.
- Any missing data will be handled using appropriate statistical imputation methods or sensitivity analyses, as described in the statistical plan.

All procedures will comply with ethical guidelines for the protection of human participants and data privacy.

13. Safety Monitoring

Although the interventions in this study are non-invasive and carry minimal risk, appropriate safety monitoring procedures will be implemented to ensure participant well-being.

Key Safety Procedures:

- All participants will be screened before enrollment to ensure eligibility and minimize risk.
- A licensed physical therapist will supervise each VR rehabilitation session to monitor physical exertion and movement quality.

- Participants will be instructed to report any signs of discomfort, dizziness, pain, or fatigue immediately during or after each session.

Adverse Event Handling:

- Any adverse events (AEs), whether mild or serious, will be documented and evaluated by the investigator.
- Participants experiencing significant AEs will be referred for medical evaluation and may be withdrawn from the study if necessary.
- A safety log will be maintained for transparency and accountability.

Regular check-ins and post-session debriefings will be conducted to ensure both physical and psychological safety throughout the study.

14. Limitations of the Study

While this study is designed with scientific rigor and careful planning, several limitations must be acknowledged:

1. Sample Size: The relatively small sample size ($n = 40$) may limit the statistical power and generalizability of the results to larger populations or different athletic groups.
2. Short Intervention Duration: The 4-week intervention period, although adequate for observing changes in ROM and pain, may not capture long-term rehabilitation outcomes or recurrence rates.
3. Single-Center Study: Conducting the study at a single university or region may introduce selection bias and limit external validity.
4. Self-Reported Pain Measures: The use of self-reported Visual Analogue Scale (VAS) scores for pain may be influenced by individual perceptions and psychological factors.
5. Participant Adherence: Although engagement is expected to be high in VR-assisted groups, individual differences in motivation, fatigue, or scheduling conflicts may affect adherence to the protocol.

Future studies with larger sample sizes, multicenter designs, longer follow-up periods, and objective pain assessments (e.g., biomarkers, neuroimaging) are recommended to validate and extend the findings.

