1.1 Synopsis

This study investigates the effectiveness of Virtual Reality (VR)-assisted rehabilitation on improving shoulder joint range of motion (ROM) and reducing pain in female collegiate basketball players with shoulder impairments. The study will compare the effects of VR-assisted rehabilitation, traditional rehabilitation, and a control group (no intervention) over a 9-week period.

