1.3 Schedule of Activities

Pre-Study Screening: July 15, 2024: Initial screening to assess eligibility (e.g., shoulder impairments, regular participation in basketball).

Intervention Period: July 15 to September 13, 2024: Participants will undergo their respective rehabilitation protocols (VR-assisted, traditional, or control).

Final Assessment: September 13, 2024: Post-intervention evaluations of shoulder ROM and pain levels.

2. Introduction

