4.4 End-of-Study Definition

The study will conclude on September 13, 2024, after all post-intervention assessments are completed.

5. Study Population

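### The intervention is stated as 9 weeks but dated as 7, cannot fit 9 weeks between randomisation and study end, and has conflicting lengths and start dates elsewhere in the protocol

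*Protocol*

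**What the plan says.** The protocol gives the length or dates of the intervention in several places.

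- **Section 1.1 (Synopsis):** the arms are compared "over a 9-week period".
- **Section 1.3 (Schedule of Activities):** "Intervention Period: July 15 to September 13, 2024". Screening is placed on July 15 and the final assessment on September 13.
- **Section 4.4:** "The study will conclude on September 13, 2024, after all post-intervention assessments are completed".
- **Section 11 (Participant Timeline):** recruitment July 15–18; baseline assessment July 19–21; on July 22, "Final baseline evaluation and randomization of participants into intervention groups"; intervention "July 22 • September 9, 2024", described as "Participants undergo 9 weeks of VR-assisted or traditional rehabilitation, or no intervention (control group"; on August 15, a "Mid-intervention check-in to assess progress, adherence, and potential adjustments"; post-intervention evaluation September 10–13.
- **Section 14 (Limitations):** "The 4-week intervention period, although adequate for observing changes in ROM and pain".

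**The concern.** The Section 11 row contradicts itself, since its dates are two weeks shorter than its stated length. The other sections do not settle which is right. Between them they give three lengths (4, 7 and 9 weeks, the 7 only through dates) and two start dates (July 15 and July 22).

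Two things are at stake. First, Sections 5.3 and 6 give no session frequency, session length or number of sessions, so calendar duration is the only quantified element of exposure in this document. It is a figure that the trial will report and that others would use to interpret or repeat it. Second, the dates are conduct instructions. The primary analysis in Section 9.3 compares ROM before and after the intervention. If sessions began on the Section 1.3 date while baseline and randomisation followed Section 11, the pre-intervention ROM and pain values would no longer be clean.

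**Working it through.** **Inputs.** All dates are in 2024 and come from the protocol: randomisation July 22 (Monday), intervention end September 9 (Monday) and post-assessment September 10–13, from Section 11; study end September 13 (Friday), from Section 4.4; alternative intervention start July 15 (Monday), from Section 1.3. Nine weeks is 9 × 7 = 63 days.

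**Step 1: the stated figure against its own dates.** July 22 to September 9 is 49 days elapsed, and 49 / 7 = 7.0 weeks. Counting both end days gives 50 days, or 7.1 weeks. The stated 9 weeks is not reproduced. The shortfall is (63 − 49) / 63 = 22%, or (63 − 50) / 63 = 21% counted inclusively.

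**Step 2: more lenient readings.**

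| Window | Days (inclusive) | Weeks (inclusive) | Monday–Friday weeks |
|---|---|---|---|
| Section 11 intervention, July 22 – September 9 | 50 | 7.1 | 7 plus one Monday |
| Randomisation to study end, July 22 – September 13 | 54 | 7.7 | 8 |
| Section 1.3 intervention, July 15 – September 13 | 61 | 8.7 | 9 |

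The second row is the most that can follow randomisation, and it absorbs the September 10–13 assessment days. It is still (63 − 54) / 63 = 14% short, and one working week short on a Monday–Friday count.

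**Step 3: where nine weeks from randomisation would end.** Sixty-three days starting on July 22 end on Sunday, September 22. Nine Monday–Friday weeks end on Friday, September 20. Both fall after the stated study end.

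**Step 4: whether Section 1.3 explains the 9 weeks.** Its dates cover nine Monday–Friday weeks, which is probably where the figure comes from. But July 15 is also the screening day in Section 1.3 and the first recruitment day in Section 11. It lies four days before the first baseline assessment and seven days before randomisation, and the window ends on the final assessment day. So it cannot be nine weeks of randomised treatment.

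**Step 5: the mid-point.** August 15 is day 24 after July 22, and half of 49 days is 24.5. The middle of nine weeks from July 22 would be August 22. This speaks against nine weeks counted from July 22. It does not choose between the Section 11 and Section 1.3 windows, because the middle of the latter is August 14.

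**Step 6: Section 14.** Four weeks is 28 days, which matches no pair of dates in the protocol.

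**The case against.** The arithmetic is hard to dispute. The best case on the other side concerns weight and remedy.

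- **No effect on inference.** The arms share one calendar, and no error rate, endpoint or estimator depends on 7 versus 9 weeks. This stands for the mislabelled length. Contaminated baselines would require mixing the two schedules. That is unlikely, because participants cannot start their allocated programme before allocation, so the risk is only conditional.
- **Calendar weeks are not dose.** Without session frequency, the 22% is a shortfall in calendar time, not in rehabilitation delivered. This also stands. It does not excuse the contradiction, because duration is all that this document quantifies.
- **Seven weeks is never stated, whereas nine appears twice.** The document does not show which length was intended. This is a fair reason for the sponsor to confirm the length before the text is changed. Still, nine weeks after randomisation is impossible on the stated dates, whereas the Section 11 sequence of baseline, randomisation, treatment and post-assessment is coherent.
- **The Synopsis may describe the whole study window.** That reading is possible for Section 1.1, but not for the Section 11 row, which ties 9 weeks to the rehabilitation itself.
- **The 4-week sentence is probably carried-over text and the mid-point is not an error.** Both are fair remarks. The sentence is nonetheless still in the protocol, and the main contradiction needs neither.

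**Conclusion.** The concern holds and should be corrected before the trial is reported. The Section 11 dates give 7.0 weeks against a stated 9, a gap of 14 days (13 if both end days are counted). With randomisation on July 22 and study end on September 13, no counting convention examined here yields nine weeks of randomised intervention, and the best case is at least 9 days short. Section 1.3 reaches nine Monday–Friday weeks only by starting treatment seven days before randomisation, and Section 14 adds a third length.

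The conclusion rests only on the protocol's dates and on taking the intervention to follow randomisation. It does not establish which length was intended or delivered. The consequence is a wrong exposure figure and conflicting start instructions, not a demonstrated bias in the comparison of arms.

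**What to change.** The sponsor should confirm the intended length and then align every statement with it.

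**Default, following Section 11:** baseline July 19–21, final baseline and randomisation July 22, intervention July 22 to September 9, post-assessment September 10–13. Change the Section 1.3 intervention dates to match and its final assessment to September 10–13. State 7 weeks in Sections 1.1, 11 and 14. If the Synopsis was meant to describe the whole study window, it should say so and give the intervention length separately.

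**If 9 weeks were intended:** end the intervention on September 22 and place post-assessment and study end after that date in Sections 1.3, 4.4 and 11.

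Under either option, report the exposure actually delivered. If the dates have already passed, the session attendance recorded under Section 12 can settle what that was.

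**Cost:** the default needs wording changes only, though the stated duration becomes shorter. The 9-week option moves the study end by more than a week and changes the calendar of a study that already has ethics approval.
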